15.2.4 Stratum 2 (Germinoma)

- If CR/CCR after 4 cycles of induction chemotherapy, low-dose radiotherapy should commence within 3 weeks of recovery from last chemotherapy (day 21) and no later than 6 weeks after the first day of the last chemotherapy cycle. If radiotherapy cannot be initiated by the above-mentioned time points, the patient will be removed from protocol therapy.
- If PR, SD, or PD after 4 cycles of induction chemotherapy, second surgery is highly recommended. If mature teratoma or non-viable tumor/fibrosis/scar is found, then low-dose radiotherapy will commence within 31 days after surgery. If the patient is found to have viable tumor other than mature teratoma, they will be removed from protocol therapy. If radiotherapy is not initiated within 31 days after surgery, the patient will be removed from protocol therapy.
- If PR or SD (> 0.5 cm suprasellar or > 1 cm pineal but ≤ 1.5 cm residual) after 4 cycles of induction chemotherapy and second surgery is not performed, moderate-dose radiotherapy will commence within 3 weeks of recovery from last chemotherapy and no later than 6 weeks after first day of the last chemotherapy cycle. If radiotherapy cannot be initiated by the above-mentioned time points, the patient will be removed from protocol therapy.

15.2.5

It is preferable to commence radiation treatments on or before a Thursday of any given week. Radiation is given 5 days a week, Monday through Friday.

15.3 Emergency Irradiation

Patients are not allowed to have received radiation therapy prior to enrollment on this protocol and urgent irradiation is not envisioned under any circumstance.

15.4 Equipment and Methods of Delivery and Verification

Equipment	Photons (any energy)	IMRT (4-10MV)	Protons
Linear Accelerator	X	X	
Proton Beam			X

15.4.1 Treatment planning

CT (volumetric) based planning is required to optimize dose to the PTV while protecting normal tissues. Organs at risk within the irradiated volume should be contoured including those required. A DVH is necessary to determine target coverage and evaluate dose to normal tissues. CT section thickness should be ≤3mm.

15.4.2 In-room verification of spatial positioning

15.4.2.1

Portal imaging is the most common system used to verify patient position, in particular when the target volume is believed to possess a fixed spatial relationship with visualized bony anatomy. If volumetric imaging is not available, orthogonal paired (AP and lateral) portal images (MV or kV) are required to verify that the isocenter is in correct alignment relative to the patient position. Beamline imaging of the treatment port should be performed when feasible. For proton treatment, orthogonal paired kV imaging for daily patient positioning and beamline kV imaging for treatment port verification are required.

15.4.2.2

Volumetric imaging is allowed in this study. This includes in-room kV or MV cone beam or conventional CT imaging. Please be able to submit representative axial images showing the isocenter and the correct alignment in relationship to the patients' position. For CT tomography where isocenters are not used, a printout of the isodoses overlaid on the fused CT images can be printed to demonstrate in room verification.

15.5 Target Volumes

15.5.1 General comments

International Commission on Radiation Units and Measurements (ICRU) Reports 50, 62 and 78 (www.icru.org) define prescription methods and nomenclature that will be utilized for this study. Although the MRI obtained immediately prior to

radiation therapy should be used for treatment planning, the target volumes for this study will be determined by the collective information that delineates the extent of disease before and after chemotherapy and second-look surgery. Patients require a combination of pre- and post-chemotherapy MR sequences to delineate the extent of disease and the ventricular volume. MR pre- and post-gadolinium contrast T1, T2, and FLAIR sequences should be reviewed. The sequences that best define the extent of initial disease and the post-chemotherapy ventricular volume should be registered to the treatment planning CT and used to determine the whole ventricular CTV and the local field boost GTV. The GTV, CTV and PTV and normal tissues must be outlined on all axial imaging slices on which the structures exist.

Practical Targeting Guidelines

After following the procedure outlined below, the investigator will have created and appropriately named six (n=6) target volumes: Whole Ventricular Volume (WVV), Whole Ventricular Volume CTV (WVVCTV), Whole Ventricular Volume PTV (WVVPTV), boost GTV (GTV), boost CTV (CTV) and boost PTV (PTV).

- (1) Obtain a treatment planning CT using a ≤ 3 mm image section thickness. Contrast is not required.
- (2) Fuse the appropriate MR sequences
- (3) Contour the GTV to satisfy the protocol requirement to delineate this volume.
- (4) Expand GTV geometrically by 5mm to create a CTV for the boost phase of treatment.
- (5) Expand the CTV geometrically by 3 or 5mm to create the PTV. Please note that a 3mm PTV margin expansion requires daily image guidance and intervention prior to treatment. A 5mm PTV margin expansion has no special requirements.
- (6) Contour the WVV to satisfy the protocol requirement to delineate this volume.
- (7) The WVV is not a volume representing gross tumor and therefore does not require a geometric expansion to form the WVVCTV. However, it is critical that the boost CTV be included in the WVVCTV to ensure the boost CTV receives the protocol specified dose. Add the boost CTV to the WVV. Please name this volume WVVCTV.
- (8) Expand the WVVCTV geometrically by 3 or 5 mm to create the WVVPTV. Please note that that a 3mm PTV margin expansion requires daily image guidance and intervention prior to treatment. A 5mm PTV margin expansion has no special requirements.
- (9) Please note that the boost volumes must be defined upfront to ensure this volume receives the protocol specified dose.

15.5.2 Photon definitions for whole ventricular volume, whole ventricular CTV and whole ventricular PTV

- A contouring atlas is available on the COG and IROC RI (QARC) websites (www.QARC.org).
- The whole ventricle volume (WVV) should encompass the lateral, third, and fourth. Care should be taken to ensure the suprasellar and pineal cisterns are included in the whole ventricle volume. Inclusion of the prepontine cistern is optional but should be considered for patients that have undergone a third ventriculostomy and for patients with large suprasellar tumors. The whole ventricles should be contoured according to the whole ventricle atlas available on the COG website and QARC website. The fusion of T2 MR sequence obtained just prior to radiation therapy to assist in delineating CSF/ventricles is encouraged.
- Whole ventricular clinical target volume (WVVCTV):
The whole ventricular volume represents an area of subclinical microscopic disease in the ventricular system and therefore a geometric margin is not required to form the WVVCTV. **However, it is critical that the WVV be combined with the boost CTV to ensure full dose to the involved field boost.** Combine the WVV and boost CTV to form the WVVCTV. The WVVCTV should not extend outside of the bony calvarium.
- Whole ventricular planning target volume (WVVPTV):
A geometric expansion of 3 or 5 mm should be added to the WVVCTV to create the WVVPTV. The PTV has two components, the internal margin (IM) and the set-up margin (SM). The IM is meant to compensate for all movements and variations in size and shape of the tissues contained within the WVVCTV. The SM is meant to account for set-up, mechanical and dosimetric uncertainties related to daily patient positioning, treatment equipment and software. Given that the WVVCTV is generally confined to the intracranial space, the WVVPTV may extend into or beyond bone but is unlikely to extend beyond the surface of the patient.

15.5.3 Photon definitions for boost volumes (GTV, CTV and PTV)

- Gross tumor volume (GTV) should include any residual tumor present at the time of treatment planning and all tissues initially involved or in contact with tumor prior to any intervention (surgery or chemotherapy). The GTV is defined as the tumor bed at the time of diagnosis accounting for shifts in normal tissues displaced by tumor that has responded to chemotherapy or has been removed by surgery. This does not apply to areas of parenchymal infiltration. Any region of the brain infiltrated by tumor should be included in the GTV.

All diagnostic imaging should be reviewed prior to treatment planning and the sequences that best define the full extent of disease should be registered for treatment planning.

- Boost clinical target volume (CTV) includes the GTV with an added margin that is meant to treat subclinical microscopic disease and is anatomically

confined (i.e., the CTV is limited to the confines of the bony calvarium, falx and tentorium where applicable or extends up to but not beyond neuroanatomic structures through which tumor extension or invasion is certain not to have occurred); the CTV margin will be 5mm for all patients. When the GTV approaches the boundary of an anatomic compartment, the CTV will extend up to and include the boundary. The CTV margin chosen for this study requires diagnostic MR imaging data with image section thickness $\leq 5\text{mm}$

- Boost planning target volume (PTV) includes a margin which is added to the CTV in 3-dimensions to create the PTV. It is geometric and not anatomically defined. The PTV has two components, the internal margin (IM) and the set-up margin (SM). The IM is meant to compensate for all movements and variations in size and shape of the tissues contained within the CTV. The SM is meant to account for set-up, mechanical and dosimetric uncertainties related to daily patient positioning, treatment equipment and software. For this study, the PTV margin should be 3 mm. Given that the CTV is generally confined to the intracranial space, the PTV may extend into or beyond bone but is unlikely to extend beyond the surface of the patient.

15.5.4 Proton definitions for GTV, CTV and PTV

- GTV is the same for protons and photons.
- CTV is the same for protons and photons.
- PTV will be uniquely defined for proton therapy ([Section 15.6.4](#)).
- When passive scattering or uniform scanning methods are used, the boost planning target volume (PTV) for proton therapy will include a margin which is added to the CTV in 3-dimensions. The margin should be consistent with the motion control and setup accuracy for the particular type of treatment at the treating proton center. **The PTV will be used for dose reporting and not specifically for treatment planning.** The goal of treatment planning will be CTV coverage at 100% directly with specific measures taken for each specific uncertainty, Specific adjustments will be made to (1) aperture margin definitions, (2) smearing of compensator, (3) range of the individual beams (depth of penetration), and (4) modulation width of the SOBP. The following parameters must be explicitly reported for each beam: range, modulation, smearing radius of the compensator, set-up margin (SM) and PTV margin. The specifics of dose reporting for the proton PTV and recommendations regarding the PTV margin are discussed in [Section 15.6.4](#).

15.6 Target Dose

15.6.1 Dose Definition

Photon dose is to be specified in centigray (cGy)-to-muscle. For proton beam, the absorbed dose is specified in Gy (RBE), which is the same as ICRU 78 DRBE using a standard RBE of 1.10 with respect to water.

15.6.2 Prescribed dose and fractionation for NGGCT Stratum 1:

- The total dose to the whole ventricular PTV prescription isodose surface will be 3060 cGy administered in 17 fractions of 180cGy. The patient should be treated with one fraction per day. All fields should be treated each day for photon treatments. It is recommended that at least 2 fields be treated per day for proton treatments. Simultaneous integrated boost is not allowed.

The total dose to the boost PTV prescription isodose surface will be 2340 cGy administered in 13 fractions of 180cGy. The cumulative dose will be 5400 cGy. The patient should be treated with one fraction per day. All fields should be treated each day for photon treatments. It is recommended that at least 2 fields be treated per day for proton treatments. Simultaneous integrated boost is not allowed.

Table 15.6.2 Radiotherapy volume and dose guidelines for NGGCT Stratum 1*

Response	Whole Ventricle Dose	IF Boost Dose	Total Dose
CR/PR	3060cGy	2340cGy	5400cGy
CR/PR after second surgery	3060cGy	2340cGy	5400cGy
Mature teratoma/fibrosis/scar and CR/PR after second surgery	3060cGy	2340cGy	5400cGy
< PR after second surgery or positive markers	Off protocol therapy	Off protocol therapy	Off protocol therapy

* The dose per fraction is 180 cGy for both whole ventricle and boost dose

15.6.3 Prescribed dose and fractionation for Germinoma Stratum 2:

- The total dose to the whole ventricular PTV prescription isodose surface will be 1800 cGy administered in 12 fractions of 150cGy, unless the patient has had a PR to chemotherapy and has not undergone second-look surgery, in which case the whole ventricular PTV prescription isodose surface will be 2400 cGy administered in 16 fractions of 150cGy. The patient should be treated with one fraction per day. All fields should be treated each day for photon treatments. It is recommended that at least 2 fields be treated per day for proton treatments. Simultaneous integrated boost is not allowed.
- The total dose to the boost PTV prescription isodose surface will be 1200 cGy administered in 8 fractions of 150cGy. The cumulative dose will be 3000 cGy, unless the patient has had a PR to chemotherapy and has not undergone second-look surgery, in which case the cumulative dose will be

3600 cGy. The patient should be treated with one fraction per day. All fields should be treated each day for photon treatments. It is recommended that at least 2 fields be treated per day for proton treatments. Simultaneous integrated boost is not allowed.

Table 15.6.3 Radiotherapy volume and dose guidelines for Stratum 2*

Response	Whole Ventricle Dose	IF Boost Dose	Total dose
CR/CCR	1800cGy	1200cGy	3000cGy
PR (> 0.5 cm suprasellar or > 1 cm pineal but ≤ 1.5 cm residual disease and no Second-Look Surgery)	2400cGy	1200cGy	3600cGy
Mature teratoma/fibrosis/scar found at Second-Look Surgery	1800cGy	1200cGy	3000cGy
Viable tumor found at second surgery or SD/PD > 1.5 cm and no Second-Look Surgery or positive markers	Off protocol therapy	Off protocol therapy	Off protocol therapy

*The dose per fraction is 150 cGy for both whole ventricle and boost dose.

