SD: Stable Disease
PD: Progressive Disease

See [Section 10](#) for specific radiographic and tumor marker definitions of CR, CCR, PR, SD and PD.

* Germinoma patients with PR, SD with > 1.5 cm residual and PD with normalization of hCGβ should be considered for second-look surgery. If histology confirms fibrosis, scar, mature teratoma or non-viable tumor, WVI to 18 Gy followed by local boost of 12 Gy to a total dose of 30 Gy will be delivered. Patients with > 0.5 cm (suprasellar) or > 1 cm (pineal) but ≤ 1.5 cm residual who do not undergo second-look surgery will be treated with WVI to 24 Gy followed by local boost of 12 Gy to a total dose of 36 Gy. If second-look surgery is not performed or patients do not meet criteria for at least PR with ≤ 1.5 cm residual disease or findings following second-look surgery indicate residual viable tumor, patients will be removed from protocol therapy.

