Patients who are unable to undergo a second-look surgery due to safety or other reasons, will be taken off protocol therapy if they do not meet criteria for PR/CR (imaging and tumor markers).

Chemotherapy for Germinoma (Stratum 2)

Week					
0	3	Evaluation	6	9	Response Evaluation
Cycle A	Cycle A	(MRI/tumor markers)	Cycle A	Cycle A	(MRI/tumor markers)

Patients will receive 4 cycles of Induction chemotherapy consisting of carboplatin and etoposide. The entire length of Induction is 12 weeks unless delay occurs due to myelosuppression or unanticipated toxicity.

Following Induction those patients in CR/CCR will undergo radiation therapy (see guidelines below).

Patients with PR, SD with > 1.5 cm residual and PD with normalization of hCGβ should be considered for second-look surgery after completion of chemotherapy. Patients with evidence of new lesion(s) and/or increase in tumor markers will be removed from protocol therapy.

- If findings following (second-look) surgery are consistent with fibrosis, scar, mature teratoma or non-viable tumor, patients will receive 18 Gy WVI followed by 12 Gy boost to the primary site in 1.5 Gy daily fractions.

- If findings following (second-look) surgery indicate residual viable malignant elements, patients will be removed from protocol therapy.

Patients who have SD or PR with > 0.5 cm (suprasellar) or > 1 cm (pineal) but \leq 1.5 cm residual disease and do not undergo a second-look surgery due to safety or other reasons, will receive 24 Gy WVI followed by 12 Gy boost to the primary site in 1.5 Gy daily fractions.

- Patients who have SD or PR with greater than 1.5 cm residual tumor or PD but are unable to undergo a second-look surgery due to safety or other reasons, will be taken off protocol.

Radiation Therapy for NGGCT (Stratum 1)

Radiation therapy will be administered to all volumes in fractions of 1.8 Gy given once daily. See [Section 10.0](#) for response definitions.

- a. CR and PR: WVI to 30.6 Gy followed by IFR boost of 23.4 Gy to a total dose of 54 Gy.
- b. Stable disease (SD) or progressive disease (PD): Off protocol therapy unless a second-look surgery renders the patient in CR or PR.

Radiation Therapy for Germinoma (Stratum 2)

Radiation will be administered to all volumes in fractions of 1.5 Gy given once daily. See [Section 10.0](#) for response definitions.

- a. CR and continuous complete response (CCR): WVI to 18 Gy followed by local boost of 12 Gy to a total dose of 30 Gy.

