- b. PR, SD and PD with normal markers: If (Second-look) surgery is consistent with no viable tumor or mature teratoma, WVI to 18 Gy followed by IFR boost of 12 Gy to a total dose of 30 Gy will be delivered. If any viable tumor (including Germinoma) is found, patients will come off protocol therapy.
- c. PR or SD with normal markers: Patients with > 0.5 cm suprasellar or > 1 cm pineal but \leq 1.5 cm residual who do not undergo second-look surgery will be treated with WVI to 24 Gy followed by local boost of 12 Gy to a total dose of 36 Gy. If second-look surgery is not performed and patients do not meet criteria for at least PR with \leq 1.5 cm residual disease, patients will be off protocol therapy.
- d. Progressive disease (PD): Patients with PD with normal serum and CSF markers after 4 cycles of chemotherapy will proceed to (second-look) surgery. If (second-look) surgery findings are consistent with mature teratoma or non-viable tumor, WVI to 18 Gy followed by IFR boost of 12 Gy to a total dose of 30 Gy will be delivered. Patients with any viable tumor (except mature teratoma) will be off protocol therapy. Patients with evidence of new lesion(s) and increasing markers or patients who do not have second-look surgery will be removed from protocol therapy.

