8.0 CRITERIA FOR REMOVAL FROM PROTOCOL THERAPY AND OFF STUDY CRITERIA

8.1 Criteria for Removal from Protocol Therapy

- a) Progressive disease with increasing markers during Induction chemotherapy.
- b) NGGCT (Stratum 1) patients with positive markers at the end of Induction chemotherapy or who have < PR after induction chemotherapy.
- c) NGGCT (Stratum 1) patients with < PR after second-look surgery or any viable tumor (except mature teratoma) after second-look surgery
- d) NGGCT (Stratum 1) patients who are unable to undergo second-look surgery due to safety or other reasons and do not meet criteria for CR/PR (imaging and tumor markers).
- e) Germinoma (Stratum 2) patients with PD and positive markers at the end of Induction chemotherapy.
- f) Germinoma (Stratum 2) patients who are unable to undergo second-look surgery due to safety concerns and they do not meet the criteria for at least PR with ≤ 1.5 cm residual disease without second-look surgery.
- g) Germinoma (Stratum 2) patients with any viable tumor (except mature teratoma, fibrosis, scar or non-viable tumor) after second-look surgery
- h) Refusal of further protocol therapy by patient/parent/guardian.
- i) Completion of protocol therapy.
- j) Physician determines it is in patient's best interest.
- k) Development of a second malignancy.
- l) Patient is enrolled but rechecked labs are outside the limits of eligibility prior to starting therapy. (See [Section 3.2](#))
- m) Radiotherapy cannot be initiated within 6 weeks after Day 1 of the last cycle of Induction chemotherapy or within 31 days after second-look surgery. (See [Sections 15.2.3](#) and [15.2.4](#)).
- n) Progressive disease with positive or increasing markers at the end of Induction chemotherapy, following second-look surgery or during radiation therapy.

Patients who are off protocol therapy are to be followed until they meet the criteria for Off Study (see below). Follow-up data will be required unless consent was withdrawn.

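### For Stratum 2 patients without second-look surgery, the protocol's passages disagree on who receives protocol radiotherapy and who leaves protocol therapy

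*Combined protocol and SAP*

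**What the plan says.** All passages concern Stratum 2 after four cycles of induction.

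- **15.6.3, dose text.** The whole-ventricle dose is 1800 cGy "unless the patient has had a PR to chemotherapy and has not undergone second-look surgery", in which case it is 2400 cGy. The second bullet repeats the condition for the total: "The cumulative dose will be 3000 cGy, unless the patient has had a PR to chemotherapy and has not undergone" second-look surgery, when it becomes 3600 cGy. Neither bullet mentions residual size. The title of Table 15.9d uses the same unrestricted category.
- **Table 15.6.3.** The partial response (PR) row without surgery stops at 1.5 cm. The off-protocol row reads "Viable tumor found at second surgery or SD/PD > 1.5 cm and no Second-Look Surgery or positive markers".
- **4.1, chemotherapy for germinoma.** "Patients who have SD or PR with greater than 1.5 cm residual tumor or PD but are unable to undergo a second-look surgery", for safety or any other reason, come off protocol.
- **4.1, radiation for germinoma, item c, and 15.1.2.** Both use the same removal condition: "If second-look surgery is not performed and patients do not meet criteria for at least PR with" a residual of at most 1.5 cm.
- **15.2.4.** The no-surgery radiotherapy path is for PR or stable disease (SD) with at most 1.5 cm residual.
- **8.1(f).** The formal removal list names "Germinoma (Stratum 2) patients who are unable to undergo second-look surgery due to safety concerns" who also fall short of PR with at most 1.5 cm.
- **Schema 2 footnote.** One sentence gives 24 Gy plus a 12 Gy boost to patients with residuals up to 1.5 cm who do not have surgery. A later one removes patients: "If second-look surgery is not performed or patients do not meet criteria for at least PR with ≤ 1.5 cm residual disease".

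**The concern.** A site must be able to place each patient without second-look surgery on exactly one path. For three response and size groups the answer depends on the page consulted.

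At stake first is treatment: the same patient is irradiated on protocol or removed from protocol therapy. There may also be an analysis consequence. Section 9.1 places in the Stratum 2 primary analysis any eligible patient who receives dose-reduced radiotherapy, and it defines the neurocognitive feasibility cohort by evaluability for that objective. If receipt of protocol radiotherapy depends on how a site reads the text, membership of those sets could depend on it too.

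**Working it through.** **1. Are the schedules themselves consistent?** Yes. From 15.6.3: 12 × 150 = 1800 cGy, 16 × 150 = 2400 cGy and 8 × 150 = 1200 cGy. The totals are 1800 + 1200 = 3000 and 2400 + 1200 = 3600 cGy, as stated. The conflict is about who gets which path.

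**2. Passages side by side, no second-look surgery, markers negative.**

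| Group | Irradiated | Removed | Not covered |
|---|---|---|---|
| PR, residual > 1.5 cm | 15.6.3, both bullets; Table 15.9d title implies it | 4.1 chemotherapy text; 4.1 item c; 15.1.2; Schema 2 footnote; 8.1(f) if the reason is safety | Table 15.6.3; outside the 15.2.4 no-surgery path |
| PR, residual ≤ 1.5 cm (above the CR limit) | 15.6.3 text and table; 4.1; 15.1.2; 15.2.4; Schema 2 footnote, treating sentence | Schema 2 footnote, removing sentence | – |
| SD, residual ≤ 1.5 cm | 4.1 chemotherapy text; 4.1 item c; 15.1.2; 15.2.4 | Schema 2 footnote, removing sentence | 15.6.3 higher-dose exception and its table name only PR; the 10.4 SD definition requires > 1.5 cm |

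The second row turns on one word. The footnote joins its two conditions with *or*, so absence of surgery alone removes the patient whom the treating sentence has just irradiated. Item c and 15.1.2 use *and*, which does not conflict with treating that patient.

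In the third row, both SD definitions in 10.4 (3-D and 2-D) require a residual above 1.5 cm, so the SD group that four passages irradiate cannot arise under the protocol's own definition. The closing sentences of item c and 15.1.2 also set a threshold of at least PR, which SD does not literally meet.

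**3. Can the first group exist?** Section 10.4 defines PR by a lower size bound and a relative decrease, with no upper bound on the residual. Assume equal shrinkage in all directions.

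- 3-D rule, volume decrease of at least 65%: the residual diameter can be up to 0.35^(1/3) = 0.705 of baseline, so the smallest baseline leaving 1.5 cm is 1.5 / 0.705 = 2.13 cm.
- 2-D rule, area decrease of at least 50%: 1.5 / 0.50^(1/2) = 2.12 cm.
- Example, 3 cm to 2 cm: volume decrease 1 − (2/3)³ = 70.4%, area decrease 1 − (2/3)² = 55.6%. This is PR by either rule, with 2 cm left.

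The group is therefore not empty by definition. The documents give no baseline size distribution and no rate of surgery, so its frequency is unknown.

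**4. Why surgery was not done.** Section 8.1(f) is limited to safety. The 4.1 chemotherapy text adds other reasons, and item c and 15.1.2 apply whenever surgery was not performed. A PR patient above 1.5 cm who declines surgery is removed by the last three but is not named in 8.1(f).

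**5. Link to the analysis set.** Section 9.1 makes receipt of dose-reduced radiotherapy the entry condition. Section 9.2.3 describes the contributing 64.7% as patients with complete or continued complete response (CR/CCR) who receive reduced radiotherapy. Under 9.1 alone the reading could change who is counted; under 9.2.3 a PR patient without surgery does not contribute on either reading.

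**The case against.** The strongest reply is that 15.6.3 only states doses. Section 15.1.2, in the same chapter, decides who is irradiated, and it removes the larger residuals. Section 15.2.4 keeps the no-surgery path to 1.5 cm or less, and the PR row just below the 15.6.3 text has the same limit. On this view the dose text omits a qualifier that is otherwise stated consistently, and a reader who applies 15.1.2 first never reaches the conflict. The gap in 8.1(f) is also narrow, because item c and 15.1.2 cover any reason, and refusal under 8.1(h) may apply.

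Much of this stands for the first group: most passages point one way. It does not make the text consistent. The prescribing section states its own, broader condition, its table omits the patient instead of correcting the text, and Table 15.9d repeats the unrestricted category. Refusal under 8.1(h) is uncertain, since surgery is only to be considered (4.1) or strongly advised (15.1.2). The reply does not touch the footnote or the SD branch.

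A reader might go further and infer that these patients are counted against the 87% null rate, and set a share of the roughly 43 patients outside the 64.7% (123 × 0.353 = 43.4) against the 79 − 73 = 6 failures the rule allows. The documents do not support that. Section 9.2.3 limits contributors to CR/CCR, and it is not stated whether 24/36 Gy counts as dose-reduced under 9.1. The 64.7% requires both response and receipt of radiotherapy, so the 43 are not simply non-responders. No share is given, and patients are not failures.

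**Conclusion.** The point holds as an internal inconsistency that should be corrected. Three groups without second-look surgery lack a single disposition: PR above 1.5 cm, PR at or below 1.5 cm, and SD at or below 1.5 cm. The certain consequence is that the page consulted can decide whether a patient receives protocol radiotherapy or is removed.

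No patient count can be put on it. The geometry shows only that the first group can exist for roughly spherical lesions above about 2.1 cm at baseline, assuming equal shrinkage in all directions; it does not show that the group is common. An effect on the primary and neurocognitive sets is possible under 9.1 and disappears if contributors are limited to CR/CCR as 9.2.3 describes. The sample size and decision rule are not called into question by this point.

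**What to change.** Reconcile the Schema 2 footnote, the germinoma parts of 4.1 (chemotherapy text and item c), 8.1(f), the SD and PR definitions in 10.4, 15.1.2, 15.2.4, both bullets and the table of 15.6.3, and the title of Table 15.9d, so that:

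- each response and size group without second-look surgery has one disposition, with the same size condition wherever it appears;
- Table 15.6.3 has a row for PR above 1.5 cm without surgery;
- SD at or below 1.5 cm is either a defined category carried through to 15.6.3 or is not referred to;
- *or* versus *and* is settled between the footnote and item c and 15.1.2;
- one wording states why surgery was not done, including in 8.1(f).

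The study committee chooses the clinical rule; this review takes no position on it. It would help if 9.1 also said whether Stratum 2 contributors are limited to CR/CCR, so that the analysis set does not depend on these passages. The cost is a wording amendment and one table row, with no extra data or patients.
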